#### Handling of Temperature Measurements

If temperature data (whether collected by subject via memory aid, 30-minute in-clinic assessment, or as part of vitals collection at exam) contain a mixture of Fahrenheit and centigrade measurements, a temperature value in centigrade will be derived from the collected measurement as follows. If the original value was recorded in centigrade, the derived temperature value will be set equal to the recorded value; if the recorded value is in Fahrenheit, the derived temperature value will be the conversion to degrees Fahrenheit.

All summaries and analyses of temperature will be presented in centigrade. However, the ‘temperature as recorded’ will be retained in the analysis dataset. The ‘temperature as recorded’ and ‘temperature in degrees centigrade’ will both be presented in the relevant data listing.

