**Table 9-a      Solicited Safety Parameters in Children Aged 4 to <9 Years**

Adverse Event	Intensity grade	Severity/Intensity
Pain at injection site	0	None
	1	Mild: Does not interfere with play and daily activities
	2	Moderate: Interferes with play and daily activities with or without treatment
	3	Severe: Prevents daily activities with or without treatment
Erythema at injection site (a)	0	<25 mm
	1	Mild: 25 – $\leq$ 50 mm
	2	Moderate: >50 – $\leq$ 100 mm
	3	Severe: >100 mm
Swelling at injection site (a)	0	<25 mm
	1	Mild: 25 – $\leq$ 50 mm
	2	Moderate: >50 – $\leq$ 100 mm
	3	Severe: >100 mm
Induration at injection site (a)	0	<25 mm
	1	Mild: 25 – $\leq$ 50 mm
	2	Moderate: >50 – $\leq$ 100 mm
	3	Severe: >100 mm
Body temperature*	Record temperature in °C/°F	
Headache	0	No headache
	1	Mild: No interference with activity
	2	Moderate: Some interference with activity with or without treatment
	3	Severe: Prevents daily activity with or without treatment
Fatigue	0	None
	1	Mild: No interference with activity
	2	Moderate: Some interference with activity
	3	Severe: Significant; prevents daily activity
Muscle aches/ Myalgia	0	None
	1	Mild: No interference with activity
	2	Moderate: Some interference with activity
	3	Severe: Significant; prevents daily activity
Joint aches/ Arthralgia	0	None
	1	Mild: No interference with activity
	2	Moderate: Some interference with activity
	3	Severe: Significant; prevents daily activity
Vomiting	0	None
	1	Mild: No interference with activity
	2	Moderate: Some interference with activity
	3	Severe: Prevents daily activity
Diarrhea	0	None
	1	Mild: No interference with activity
	2	Moderate: Some interference with activity
	3	Severe: Prevents daily activity

\* = Fever is defined as greater than or equal to 38°C (100.4°F) regardless of method used [33]. Body temperature will be collected and recorded, preferably using the same method throughout the trial for a subject. The site staff will record the actual temperature route taken on the CRF. Note that identification of fever, as a solicited AE will be accomplished in the study database, based on actual temperature measurements. (a) Record greatest surface diameter in mm in the Diary.

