### 7.11.1 Adverse Events

#### In-Clinic Assessments of Reactogenicity

In-clinic 30-minutes post-vaccination assessments of reactogenicity AEs include local events (injection site pain, erythema/redness, induration, and swelling) and systemic events (headache, fatigue, myalgia, arthralgia, vomiting [number per day/intensity] and diarrhea [number per day/consistency] for children aged 4 to <9 years; and irritability/fussiness, drowsiness, loss of appetite, vomiting [number per day/intensity], and diarrhea [number per day/consistency] for children aged 6 weeks to < 4 years). Severity of injection site pain and of the systemic events is assessed in-clinic as mild, moderate or severe according to Protocol Tables 9a (age 4 – 9 years) and 9b (age 6 weeks to <4 years). Measurements of the largest diameter for injection site erythema/redness, swelling, and induration are collected. These measurements will be used to derive severity grades based on the criteria included in [Appendix A](#) and [Appendix B](#).

Temperature measurements are also collected and a systemic event of ‘fever’ will be derived as Yes/No based on temperatures  $\geq$  38 degrees centigrade [3]. Temperature levels will also be categorized in 0.5 degree intervals (centigrade). Number and percent of subjects with reactogenicity events 30-minutes post vaccination will be summarized for each vaccine administered, for each local and systemic event, and by severity.

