### **7.13 Changes in the Statistical Analysis Plan**

#### *Changes from the Analyses Planned in Protocol Version 3.0, 1 March 2016*

Section 13.1.4 of the Protocol (Version 3.1) referred to exclusion of biologically implausible measurements. Large or implausible outlying values may be identified by medical reviewers during blind data review and queried before database lock. However, no criteria to identify implausible measurements will be defined in this SAP. Due to the age range of the subjects and the multi-regional settings in this trial, a reliable and consistent cut-off for implausible measurements cannot be developed. Hence all values in the database at time of database lock will be included in the analyses.

Section 6.1 in the study protocol indicated that two interim analyses are to be performed after the primary safety and immunogenicity data are available (ie, Day 57 for Cohort 1 and Day 140 for Cohort 2). Cohort 1 consists of 3 age groups enrolled in age step-down fashion. However due to delay in availability of investigational product, enrollment of Group 3 has been delayed. Therefore, the Day 57 interim analysis of Cohort 1 will proceed on schedule but will initially include only age groups 1 and 2. After study enrollment resumes, Day 57 interim analyses of Group 3 will be provided at a later time.

[figure not shown]

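### The SAP's temperature rule converts Fahrenheit readings to Fahrenheit, not centigrade: wrong as written, with clear intent and low practical severity

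*SAP*

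**What the plan says.** The conversion rule is in SAP 7.1, Handling of Temperature Measurements. It covers diary readings, the 30-minute in-clinic reading and vital signs, and applies when the data mix the two units.

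- Purpose: "a temperature value in centigrade will be derived from the collected measurement as follows".
- Centigrade readings: "If the original value was recorded in centigrade, the derived temperature value will be set equal to the recorded value".
- Fahrenheit readings: "the derived temperature value will be the conversion to degrees Fahrenheit".
- Reporting unit, in the next paragraph: "All summaries and analyses of temperature will be presented in centigrade". The listing is to show the recorded and the centigrade values together.

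Fever is then derived by program. In SAP 7.11.1 it "will be derived as Yes/No based on temperatures" of at least 38 degrees centigrade, for both in-clinic and diary readings, and temperatures are also grouped in half-degree centigrade bands. Protocol Table 9-a gives the threshold in both units: "Fever is defined as greater than or equal to 38°C (100.4°F) regardless of method used". Table 9-b has the same threshold. Both tables allow either unit to be recorded.

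Protocol 13.1.4 provides for implausible measurements to be left out, with a body temperature above 42°C as its example, and refers to the SAP for the criteria. SAP 7.13 declines to set any, so "all values in the database at time of database lock will be included in the analyses".

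**The concern.** The Fahrenheit clause is the only conversion instruction in the SAP, and it names the wrong target unit. It is an operative derivation rule. Body temperature is a primary safety endpoint (Protocol 5.2.1, SAP 5.1), and the primary objective includes comparing the formulations' safety profiles. The derived value feeds the fever flag, the half-degree bands and the vital-sign changes from baseline.

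An unconverted Fahrenheit number compared with 38 always passes. The Protocol's example cut-off would have removed such a number from the analysis; under SAP 7.13 it stays in. A recorded 98.6°F is also a normal reading, so a query aimed at recorded values need not pick it up: the error would arise in the derivation.

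**Working it through.** **Inputs.** Fever threshold 38°C = 100.4°F (Protocol Tables 9-a and 9-b). Fever if at least 38 degrees centigrade (SAP 7.11.1). Example implausibility limit 42°C (Protocol 13.1.4). About 15 subjects per formulation/dose combination in each Cohort 1 group and about 45 in Cohort 2 (Protocol 6.1, SAP 4.4).

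**Step 1: reproduce the Protocol's pair.** F = C × 9/5 + 32, so 38 × 9/5 + 32 = 100.4. In reverse, (100.4 − 32) × 5/9 = 38.0. The stated threshold is consistent in both units.

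**Step 2: apply the SAP clause literally, then correctly.** A literal conversion of Fahrenheit to Fahrenheit leaves the number unchanged. Assume that number is stored as the derived centigrade value.

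| Recorded (°F) | Literal value | Literal fever flag | (F − 32) × 5/9 | Correct fever flag |
|---|---|---|---|---|
| 97.0 | 97.0 | Yes | 36.1 | No |
| 98.6 | 98.6 | Yes | 37.0 | No |
| 99.5 | 99.5 | Yes | 37.5 | No |
| 100.3 | 100.3 | Yes | 37.9 | No |
| 100.4 | 100.4 | Yes | 38.0 | Yes |
| 102.2 | 102.2 | Yes | 39.0 | Yes |

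Every 0.1-degree step from 95.0 to 107.9°F is flagged under the literal rule. To escape the flag, a reading would have to be below 38°F, which is (38 − 32) × 5/9 = 3.3°C. The other literal reading, applying the centigrade-to-Fahrenheit formula to the Fahrenheit number, turns 98.6 into 98.6 × 9/5 + 32 = 209.5, which is also flagged.

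**Step 3: the dropped cut-off.** All these literal values exceed 42. The Protocol's example limit would have excluded them; under SAP 7.13 they are analysed.

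**Step 4: size per child.** One afebrile child wrongly flagged adds 1/15 = 6.7 percentage points in a Cohort 1 group arm, or 1/45 = 2.2 points in a Cohort 2 arm. The addition is zero if the child had a true fever in the same interval.

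**Step 5: size by Fahrenheit share (assumed).** The documents give neither the share s of Fahrenheit readings nor the true fever rate t. Per reading, the derived rate is s + (1 − s) × t.

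| s | t = 2% | t = 5% | t = 10% |
|---|---|---|---|
| 0% | 2.0% | 5.0% | 10.0% |
| 5% | 6.9% | 9.8% | 14.5% |
| 10% | 11.8% | 14.5% | 19.0% |
| 25% | 26.5% | 28.8% | 32.5% |
| 50% | 51.0% | 52.5% | 55.0% |

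For example, with s = 10% and t = 5%: 0.10 + 0.90 × 0.05 = 14.5%. These are rates per reading and only illustrate scale; the SAP tabulates percentages of subjects.

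**The case against.** The strongest reply is that this is a proofreading slip with only one workable reading. Converting Fahrenheit to Fahrenheit is not an operation, and the lead-in, the reporting unit and the name of the listed variable all say centigrade. The fever rule also carries its unit: a value still labelled 98.6°F is not at or above 38°C. A false fever therefore needs two steps, coding the clause literally and then treating the result as centigrade. This largely stands, and it is why the severity is low. It does not make the clause correct, and the second step is easy to take because the section itself calls the output a centigrade value.

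A reader might also infer that nothing downstream would catch the error. The documents do not support that. SAP 7.13 lets medical reviewers identify and query outlying values during blinded review, although that is discretionary and may look only at recorded values. The listing would show 98.6 both as recorded and as centigrade. The half-degree bands would run into the nineties. The descriptive summaries of vital-sign temperature (SAP 7.11.3, with minimum and maximum under 7.1) would show impossible maxima. What is true is narrower: no pre-specified numeric rule would remove the value. Dropping that rule is a disclosed change with a stated reason, and is a separate matter from the wrong word.

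**Conclusion.** The clause is wrong as written and should be corrected; its practical severity is low. It contradicts its own section, the fever rule in SAP 7.11.1 and the two-unit threshold in the Protocol.

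It is tempting to conclude that every Fahrenheit reading in this trial will be reported as a fever. The documents do not show that. The result follows only if the clause is coded literally, the output is carried as centigrade, Fahrenheit readings occur, and none of the available checks reveals the error. The 6.7-point and 2.2-point figures are the effect of one wrongly flagged child under those conditions. They are not forecasts, and the effect is zero if all readings are in centigrade.

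**What to change.** In SAP 7.1, replace the last word of the Fahrenheit clause with centigrade and state the formula C = (F − 32) × 5/9. Add a rounding convention that makes 100.4°F equal 38.0°C, as in the Protocol; rounding to one decimal does this and leaves 100.3°F at 37.9°C. State that the existing fever rule and the half-degree bands are applied to this converted value.

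The cost is one word, a formula and a sentence in the SAP. No data collection, endpoint or fever threshold changes.

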#### Baseline Definition and Windowing Conventions

Study Day 1 is defined as the date of the first vaccination, as recorded on the eCRF vaccination page. Other study days are defined relative to Study Day 1, with Day -1 being the day prior to Day 1. In addition, day relative to vaccination will be derived for each vaccination dose. For example, day relative to the first dose will be equal to the Study Day. Day relative to the second dose will start with a value of 1 on the day of the second dose and so on for each vaccination given. Day relative to dose is of use for tables presenting summaries of events relative to dose.

For listings presenting observations or events by day, both the Study Day and Day Relative to Dose will be presented.

Baseline is defined as the last non-missing measurement taken before the first dose of vaccination (Day 1), unless otherwise defined for a particular endpoint parameter.

A windowing convention will be used to determine the analysis value for a given study visit for observed data analyses. The window definitions as outlined below in [Table 7.a](#) and [Table 7.b](#) will be used for the immunogenicity (serology and CMI) and vital signs, respectively. The window conventions are:

1. A window of +/- 7 days from the target day is applied to the following visits: Study Days 29 and 57 for cohort 1 and Study Days 56, 84, 112, and 140 for cohort 2;
2. A window of +/- 28 days from the target day is applied to the following visits: Study Day 210 for cohort 1 and Study Day 293 for cohort 2.

The windows for immunogenicity are constructed by dosing period relative to actual dosing day. Windows for vital signs are constructed relative to the actual study day.

One or more results for a particular immunogenicity or vital sign variable may be obtained in the same visit window (see study window definitions in [Table 7.a](#) and [Table 7.b](#)). In such an event, the result with the date closest to the expected visit date will be used. In the event that 2 observations are equidistant from the expected visit date, the later observation will be used.

**Table 7.a Visit Windows for Immunogenicity by Visit**

Cohort	Period	Visit	Day Relative to Dose within the Period (b)	Visit Window (Study Day)	
				Serology	CMI and Avidity (c)
1	Period 1 (Relative to Dose 1)	Baseline (a)	≤1	≤1	≤1
		Day 29	29	22 – 36	22 – 36
	Period 2 (Relative to Dose 2)	Day 57	29	22 – 36	22 – 36
		Day 210	182	154 – 210	---
2	Period 1 (Relative to Dose 1)	Baseline (a)	≤1	≤1	≤1
		Day 56	56	49 – 63	49 – 63
	Period 2 (Relative to Dose 2)	Day 84	29	22 – 36	22 – 36
		Day 140	29	22 – 36	22 – 36
	Period 3 (Relative to Dose 3)	Day 293	182	154 – 210	---

- (a) Where time is available, the time of the collection must be prior to the first dose of study drug. Day 1 observations taken after the first dose are considered post-baseline values.
- (b) For each period, the administration of the study drug is designated as Study Day 1. For analyses within a period, the study day value is incremented by 1 for each date following the vaccine administration. Dates prior to the vaccine administration are decremented by 1, with the date preceding the vaccine administration designated as Study Day -1 (there is no Study Day 0).
- (c) CMI is measured only for Cohort 1.

**Table 7.b Visit Windows for Vital Signs by Visit**

Cohort	Visit	Visit Window (Study Day)	
		Vital Signs	
1	Baseline (a)	≤1	
	Day 29	22 – 36	
2	Baseline (a)	≤1	
	Day 56	49 – 63	
	Day 112	105 - 119	

- (a) Where time is available, the time of the collection must be prior to the first dose of study drug. Day 1 observations taken after the first dose are considered post-baseline values.

#### *In-Clinic Reactogenicity Assessments and Diary Data*

On vaccination days, at 30 minutes following the dose, in-clinic assessments of reactogenicity (solicited local and systemic AEs) and temperatures are collected onto the eCRF. These data are only collected on vaccination days so visit window rules do not apply.

**CONFIDENTIAL**

In addition, solicited local and systemic AEs and body temperature are recorded daily (by diary) by the subject's legal guardian for 7 days following each dose (day of dose plus 6 additional days). These data are collected at the study visit following the dose and contain entries by day within that interval. Visit window rules will not be applied to the diary data; they will be summarized by diary day (and within specified diary day intervals, eg, 1-7, 1-3, 4-7) following vaccination.

## 7.2 Analysis Sets

The analyses sets are defined as follows:

Safety Analysis Set: all subjects who receive at least 1 dose of vaccine (NoV GI.1/GII.4 bivalent VLP vaccine or control vaccine).

Full Analysis Set (FAS): all subjects who are randomized and have at least 1 NoV GI.1/GII.4 bivalent VLP vaccine injection.

Per-Protocol Analysis Set (PPS): all subjects who receive the planned vaccination and do not have major protocol violations will be included in the PPS. A major protocol violation is defined as a protocol deviation that is considered to have a significant impact on the immunogenicity results of the subject. All major protocol violations will be identified prior to unblinding from review of study monitoring deviation logs and through programmatic review of blinded data, based on pre-specified criteria. Clinical judgment from Takeda will be necessary to classify each deviation as a “major” violation or not. The major protocol violation criteria will be finalized as part of the blind data review prior to the interim analysis (Day 57 for Cohort 1 and Day 140 in Cohort 2) and may include:

- 1) Not meeting entry criteria, based on selected inclusion/exclusion criteria (exclusion criteria #6 and #7) defined in protocol sections 7.1 and 7.2;

Exclusion criterion #6: Known or suspected impairment/alteration of immune function, including the following:

- a) Children <18 months of age with history of repeated episodes of acute otitis media (AOM) in the first 6 months of life (AOM defined as a bulging tympanic membrane) and not to be confused with otitis media with effusion (OME).
- b) Chronic use of oral steroids (equivalent to 20 mg/day prednisone for  $\geq 12$  weeks /  $\geq 2$  mg/kg body weight /day for  $\geq 2$  weeks) within 60 days prior to Day 1 (use of inhaled, intranasal, or topical corticosteroids is allowed).
- c) Receipt of parenteral steroids (equivalent to 20 mg/day prednisone  $\geq 12$  weeks /  $\geq 2$  mg/kg body weight /day for  $\geq 2$  weeks) within 60 days prior to Day 1.
- d) Receipt of immunostimulants within 60 days prior to Day 1.
- e) Receipt of parenteral, epidural, or intra-articular immunoglobulin preparation, blood products, and/or plasma derivatives within 3 months prior to Day 1 or planned during the full length of the trial.

- f) Receipt of immunosuppressive therapy within 6 months prior to Day 1.
- g) Human immunodeficiency virus (HIV) infection or HIV-related disease.
- h) Chronic Hepatitis B or C infection.
- i) Heritable immunodeficiency.

Exclusion criterion #7: Abnormalities of splenic or thymic function.

- 2) Receiving wrong treatment.
- 3) Receiving prohibited therapies in the following categories (also specified in protocol Section 9.1.2):
  - Parenteral immunoglobulin preparation, blood products, and/or plasma derivatives within 3 months of the first vaccination.
  - Immunosuppressive therapy within 6 months or systemic (eg, oral or parenteral) corticosteroid treatment within 60 days prior to vaccine administration or planned during the trial period.
- 4) Significant deviation from protocol-specified dosing and/or sample collection regimen as subject to pre-lock blinded medical review.
- 5) Not receiving all planned doses of the investigational vaccine.
- 6) Did not have evaluable blood sample at Baseline and Day 57 (for subjects from Cohort 1) and Baseline and Day 140 (for subjects from Cohort 2).
- 7) Other major violations, which may be identified during blinded data review prior to the interim analysis (Day 57 for Cohort 1 and Day 140 in Cohort 2) and study completion (Day 210 in Cohort 1 and Day 293 in Cohort 2).

The primary population for immunogenicity analyses will be based on the PPS. Supportive immunogenicity analyses on the primary and key secondary endpoints will also be performed using FAS. All safety analyses will be based on the Safety Analysis Set. Subjects excluded from any of the analysis datasets will be listed with the reason for exclusion in the final clinical study report. Major violations resulting in exclusion from the PPS will also be summarized by reason for exclusion.

### 7.3 Disposition of Subjects

Disposition of all screened subjects will be summarized descriptively, including a summary of the number of screened subjects and the number of randomized subjects by group. The primary reasons for ineligibility for randomization will be summarized by group. The number of randomized patients by treatment arm and center, and analysis populations by group and formulation/dose combination will also be presented.

Disposition for all randomized subjects will be summarized by the 8 formulation/dose combinations within each group and cohort. Disposition categories include:

- Number of randomized subjects and number of randomized subjects but not dosed;
- Number of subjects completing the vaccine regimen/study visits;
- Number of subjects who prematurely discontinued the vaccine regimen/study visits;
- Primary reason for premature discontinuation of the vaccine regimen/study visits.

Primary reason for premature discontinuation of the vaccine regimen/study visits will be summarized. For interim analysis, a subject is to be assumed ongoing unless he/she completed the end of study eCRF page for Day 210 (cohort 1) or Day 293 (cohort 2), indicating either completion or early termination.

Protocol deviations pertaining to study conduct are routinely collected and reviewed as part of study monitoring. These deviation logs are maintained by study management. Non-minor deviations will be transferred to the clinical data base and presented in the subject data listings. As described in Section 7.2 (under PPS), deviations will also be reviewed as part of blinded data review prior to interim and final data locks to determine if any deviation constitutes a major protocol violation.

#### **7.4 Demographic and Baseline Characteristics**

Age, gender, race, and other baseline characteristics will be summarized descriptively by formulation arm and dose group, overall and separately for each of the groups in the cohorts, for randomized subjects and subjects in the PPS. Baseline characteristics will include the numbers and percentages of subjects with Baseline (pre-vaccination) values of antibody titers below the LLoQ for each assay (Pan-Ig, HBGA, and IgA) for each VLP antigen (GI.1 and GII.4). In addition the number and percentage of subjects with values below the LLoQ for all assays and antigens will be provided.

